5.4 BLINDING STATUS OF RESEARCHERS

Researchers (outcome assessors) will be blind to group allocation when baseline interviews with male participants and their current or ex female partners are conducted. After the men are baselined from each PDU/ JSWT and their (ex)-partners have been completed their baseline assessment or declined to take part in the research or were not contactable, they will be informed of allocation. Probation practitioners and principal investigators/other staff at PDU/ JSWT will be blind during eligibility and consent.

Individual blinding status	Blinded	Unblinded
Chief Investigators	X	
Principal Investigators and all other PDU/JSWT staff at site (blinded until post baseline)		X
Co-applicants ^α	X	
Trial Manager		X
Facilitators		X
Senior Trial Statistician	X	
Trial Statistician ^a	X	
Senior Health Economist	X	
Health Economist (blinded until after data collection)	X	
Trial Participants		X
Outcome Assessors (blinded during baseline interview)		X
Partner Support Workers		X
Trial Steering Committee (TSC)	X	
Data Monitoring Committee (DMC)		X

Table 6. Blinding Status

^aThe blinding status of the research team is detailed in Table 6 above. Note the Trial Statistician will become partially blinded at the point of reporting to the Data Monitoring Committee outcome and safety data partitioned in groups labelled A and B. The time of when this planned change in blinding status of the Trial Statistician is will be reported. The Clinical Lead (co-applicant [name]) will be unblinded.

5.5 EMERGENCY UNBLINDING

Not appropriate as PIs and site staff will be unblinded to the allocation once baseline measures have been collected.

 $[*]For \ roles \ not \ listed \ please \ refer \ to \ study \ delegation \ logs.$

6. DATA MANAGEMENT

Information with regards to the study participants will be kept confidential and managed in accordance with UK data protection laws (meaning the Data Protection Act 1998 until 24 May 2018, and from 25 May 2018 the EU General Data Protection Regulation (GDPR) and applicable UK legislation that enshrines GDPR into UK law) and the Research Ethics Committee (REC) approval.

Data generated by the researchers will be stored and managed on a King's College London (KCL) SharePoint https://emckclac.sharepoint.com/sites/IOPPNaip. The primary function of SharePoint is the online file storage for secure collaborative working with the other researchers on the trial. Any work practice which involves storing, sharing, or archiving data and documents can be supported by SharePoint, helping to reduce reliance on local storage (e.g. hard-drives) and emails, whilst improving data retention practices, collaboration between individuals, compliance, and flexible working.

A "data risk model" for the data to be stored on SharePoint determine the Risk Profile Class III. With SharePoint files are stored in the cloud and protected by both Microsoft and King's College London IT. SharePoint is backed up daily. The research team external to KCL will be given access. Restricted access to research participants' personal data will be established to contact to follow up or send out reports of findings at the end of the trial. Names and contact details of consenting participants will be stored on a secure password protected folder on SharePoint user-based permissions for authorised researchers only to access these data, for the purposes of assisting in follow-ups during the trial. Personal data will be stored separately from research data on a secure password protected folder on SharePoint to allow researchers to arrange interviews during the study. With participant's consent, personal details will be stored for 10 years to allow future data linkage to determine longer term outcomes of ADVANCE-D. Names and contact details will also be used to send out a summary report at the end of the study if participants want one.

6.1 DATA MANAGEMENT

There are two datasets in the trial: the KCTU randomisation dataset and the KCTU eCRF system dataset. The CI will act as custodian for the trial data. The KCTU eCRF will have two databases – one for research data and a therapy database. Personal identifier information needed to contact participants for follow up and for data linkage will not be held in the research database. Data will be transcribed from the source to the eCRF system, ideally within 7 days of the study visit. Participant year of birth and age will be entered into the systems. No more identifiable data will be entered into the eCRF system. Trial sites will maintain a master participant log linking participant identifiers to study numbers. No data will be entered unless a participant has signed a consent form to participate in the trial. More details of the data coding will be available in the statistical analysis plan.

Source data worksheets will be supplied to all recruiting sites by the co-ordinating centre for the region. These will be prepared after the database specification is finalised and database testing is complete. Participating Sites will complete source data location lists defining the source data at their site.

6.2 DATA SECURITY

The clinical trial will involve the sharing of deidentified data of subjects for research purposes, both during and after the trial for the purposes of monitoring and analysis. All applicable statutory requirements and mandatory codes of practice in respect of confidentiality (including, where applicable, medical confidentiality) in relation to such trial subjects or their legal guardians.

Data Management Plans will be provided to the Trial Manager, detailing relevant security information about both data systems. Systems access will be strictly restricted through user-specific passwords to the authorised research team members. It is a legal requirement that passwords are not shared, and that only those authorised to access the system are allowed to do so. If new staff members join the study,

a user-specific username and password must be requested and a request for access to be revoked must be requested when staff members leave the project.

All record linkage will require a data protection impact assessment to be completed and a data sharing agreement to be in place.

6.3 DATA QUALITY PROCESSES

At the database design stage, validations will be programmed into the systems to minimise data entry errors by querying the data entered in real time with sites. The CI team will undertake appropriate reviews of the entered data, in consultation with the project analyst, where appropriate for the purpose of data cleaning and will request amendments to the eCRF system data as required. No data will be amended independently of the study site responsible for entering the data.

No data can be amended in the randomisation system, however the CI or delegate (e.g., Trial Manager) may request King's Clinical Trials Unit to add notes against individual participant entries to clarify data entry errors. Any errors should be reported by site staff to the Trial Manager as soon as possible once they are detected. The trial manager will onward report errors to KCTU and retain records in the Trial Master File.

The KCTU will provide the Trial Manager with Data Management Plans for both the eCRF system and the randomisation system once the systems are made live. Those documents will be filed in the Trial Master File. A regular Data Management Report will be produced by KCTU and passed to the Trial Manager, who will raise Data Clarification Requests (DCRs) with sites in the eCRF system. The Trial Manager will raise DCR's. Study sites will periodically review raised DCR's and respond to the queries raised.

During site monitoring visits, the trial manager will raise any queries with sites via the Source Data Verification (SDV) function.

6.4 DATABASE LOCK

At the end of the trial, the site PI's will review all the data for each participant in the eCRF system and provide electronic sign-off to verify that all the data are complete and correct.

The trial manager will confirm all checks are complete and all monitors queries have been resolved prior to database lock after 12 month data collected. At this point, with the agreement of the senior statistician, all data can be formally locked.

When the final data extract is requested, KCTU will remove all data entry user access prior to data extract and will retain only 'monitor' access for site PI's and other relevant individuals. Upon request, KCTU will provide a copy of the final exported dataset to the CI in .csv format and the CI will onward distribute to sites as appropriate. Once sites have received copies of their individual datasets and confirmation of receipt has been received, the Trial Manager will request that all user access is removed from the eCRF system. A copy of the dataset will be stored in the Trial Master File at the end of the study.

7. ADVERSE EVENT MANAGEMENT AND REPORTING

An Adverse Event (AE) is any untoward medical occurrence in a participant taking part in a research study, including occurrences which do not necessarily have a causal relationship with the research. All adverse events will be recorded in the participant's notes, the study source data worksheets and the eCRF. SAE's will be additionally reported, within 24 hours of site becoming aware of the event, to KCTU. All SAEs will be reported immediately (and certainly no later than 24hrs) as per the instructions on the SAE report form.

The sponsor will report SAEs and/or suspected unexpected serious adverse reactions as required to regulatory authorities, investigators/institutions, and the ethics committees in compliance with all reporting requirements according to local regulations and good clinical practice.

- Serious Adverse Event (SAE): Any adverse event that:
 - o results in death
 - o is life-threatening
 - o required hospitalisation or prolongation of existing hospitalisation
 - o results in persistent or significant disability or incapacity
 - o consists of a congenital anomaly or birth defect

The CI will be notified of any incidents as soon as possible. All incidents and resulting actions will be recorded in an incident report form and resulting actions will be emailed to the Trial Manager who will store these on SharePoint. No personal data will be recorded on the form. A cumulative review of all safety information by the DMC will be made on a six-monthly basis.

7.1 EVALUATING SAES OR ADVERSE INCIDENTS

7.1.1 ASSESSMENT OF INTENSITY

The Investigator will make an assessment of intensity for each SAE and adverse incident reported during the study. The assessment will be based on the Investigator's clinical judgement. The intensity of each SAE and adverse incident recorded in the eCRF should be assigned to one of the following categories:

- o Mild; An event that is easily tolerated by the participant, causing minimal discomfort and not interfering with everyday activities
- o Moderate; An event that is sufficiently discomforting to interfere with normal everyday activities
- o Severe; An event, which is incapacitating and prevents normal everyday activities

7.1.2 ASSESSMENT OF CAUSALITY

The Investigator is obligated to assess the relationship between ADVANCE-D and the occurrence of each SAE or adverse incident. The Investigator will use clinical judgment to determine the relationship. Alternative causes, such as natural history of the underlying diseases, concomitant therapy, other risk factors, and the temporal relationship of the event to ADVANCE-D will be considered and investigated.

The causal relationship to the study product assessed by clinical lead should be assessed using the following classifications:

- Not Related:
- Unlikely:
- Possible:
- Likely:
- Definitely:

There may be situations when an SAE has occurred, and the Investigator has minimal information to include in the initial report to the Sponsor. However, it is very important that the Investigator always assesses causality for every event prior to transmission of the SAE form to the Sponsor. The Investigator may change his/her opinion of causality considering follow-up information, amending the SAE form accordingly. The causality assessment is one of the criteria used when determining regulatory reporting requirements.

7.1.3 FOLLOW-UP OF AES AND SAES

After the initial SAE or adverse incident report, the Investigator is required to proactively follow each participant and provide further information to the Sponsor on the participant's condition. All reports documented at a previous visit/contact and are designated as ongoing, will be reviewed at subsequent

visits/contacts. All reports will be followed until resolution, until the condition stabilises, until the event is otherwise explained, or until the participant is lost to follow-up. Once resolved, the adverse event log will be updated. The Investigator will ensure that follow-up includes any supplemental investigations as may be indicated to elucidate the nature and/or causality of the SAE or adverse event. This may include consultation with other health, social or criminal justice professionals. New or updated information will be recorded on the originally completed SAE form, with all changes signed and dated by the Investigator. The updated SAE form should be resent to the Sponsor.

7.1.4 POST-STUDY SAES AND ADVERSE INCIDENTS (AI)

A post-study SAE or adverse incident is defined as any event that occurs outside the SAE/AI detection period. Investigators are not obligated to actively seek SAEs/AIs in former study participants. However, if the Investigator learns of any SAE or AI, including death, at any time after a participants has been discharged from the study, and he/she considers the event reasonably related to the investigational product, the Investigator will promptly notify the Sponsor.

7.2 ADVERSE EVENT PROCESSING RESPONSIBILITIES

The Trial Manager will provide a blinded report to the DMC. The Trial Statistician will report relevant adverse events to the Data Monitoring Committee.

8. SAFEGUARDING

8.1 SAFEGUARDING PROTOCOL

If the participant discloses information which indicates a risk of death or serious harm, either to themselves or others (e.g. their children), researchers will break confidentiality and disclose this information to the duty worker at the probation/social work PDU/ JSWT where the male participant attends, the women's support worker or to relevant authorities. If the participant does not consent to the sharing of this information, it may be necessary to break confidentiality. If participants do describe current/future intent to harm themselves or others, the researcher will be under obligation to ensure the incident is reported to the service staff (e.g. PP/ JSW or women's support worker) where the participant is receiving care, preferably with the participant present. Staff will then follow their usual safeguarding protocol under their duty of care. In addition, researchers and staff will report to the ADVANCE-D clinical lead to review safeguarding issues as they arise. Male participants will be interviewed in PDU/ JSWT. Female participants will be interviewed in treatment or support services, children centres or libraries. If a participant discloses current or future intent to harm themselves or others, the researcher will:

- Stop the interview and provide sympathetic and non-judgemental recognition of any emotional distress the participant is expressing.
- If safe to do so, inform the participant that what they have said will need to be shared with their PP/JSW (if available) or duty worker, or the women's support worker at the service where the interview is taking place, or the relevant authorities. If it is possible and safe to do so, the participant should stay in the PDU/JSWT or on the phone if online.
- Discuss the nature of the disclosure with the key/duty worker or women's support service, with the participant present.
- PP/ JSW or women's support service will follow their services' protocol on safeguarding and conduct a risk assessment.
- The Chief Investigator will be informed; and an adverse events form will be completed. The Ethics Committee will be informed if the adverse event is serious.
- All adverse events forms will be stored on SharePoint. Adverse events forms contain only participant ID numbers not participants' names.

To ensure that the women and their children are safe, staff from the PDU/ JSWT that their current or expartner is attending and the women's support worker will talk to each other on a regular basis to share information that relates to the women's safety and risk. This helps to ensure that work with perpetrators attending the intervention is informed by current understanding of survivors' experiences.

8.2 PARTICIPANT DISTRESS PROTOCOL

Talking about past or current violence in a relationship may make participants feel upset. If this happens, participants will be given the opportunity to speak to a PP/JSW at the PDU/JSWT or to women's support services (women only) about how they feel if they wish to, at that time or in the future. All participants will be provided with a range of local contact numbers and services that will be able to help after each research assessment/interview. We have developed a distress protocol. If any participant (male or female) involved in the research becomes upset as a result of their involvement in the study, the researcher will:

- Stop the interview and provide sympathetic and non-judgemental recognition of any emotional distress the participant is expressing.
- Refer the participant back to their PP/ JSW; or women's support worker (if interviewed at a ISS).
- If a participant discloses an immediate intention to harm themselves or others, the *safeguarding protocol* will be followed (see under Limitations to Confidentiality above).
- The researcher will call the Chief Investigator ([name], KCL) on her mobile (or a designated deputy from the co-investigators if the Chief Investigator is on leave) to inform them of the event and the action taken.
- On returning to the office, an incident form describing the disclosure and the action taken will be completed by the researcher using only the participant ID. The Ethics Committee will be informed if the adverse event is serious.
- All incident forms will be stored on SharePoint. Incident forms contain only participant ID number not participant name.

Participants who have a court order preventing them or someone on their behalf from contacting a current or former partner (e.g. restraining order/bail restriction/exclusion order/non molestation order etc.) will be ineligible. This will be based on self-report by the perpetrator in the first instance (but confirmed where possible by his current or ex-partner and the substance use treatment service). The man's keyworker at the substance use treatment service will make the final decision on whether the man is suitable to take part in the study.

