Note: A court can impose a DRR for any substance that is included in the Misuse of Drugs Act 1971. It is up to the court to decide Note: A court can impose a DRR for any substance that is included in the Misuse of Drugs Act 1971, it is up to the court to decide if they think that any substance used by a person is covered by this. However, a DRR can only be imposed if there is a test for the drug of choice available in the community. There is no test routinely available for Psychoactive Substances (PS) in the community currently. The court would need to be advised that making a person who only used PS subject to a DRR would not meet the requirements to impose such an intervention. Most people are poly drug users. If someone presents as using any substance that can be tested for (Opiates, Occaine, Amphetamines, Beroodiazepine and Cannabis) in combination with the above, a DRR can be recommended if agreed with a Treatment Provider.

[figure not shown]
Table 2. Suitability screening tool for substance use interventions

Probation Practitioners (England)/ Justice Social Workers (Scotland) check men's eligibility

In England, Probation Practitioner completes Offender Assessment System (OASys), SARA v2 and sentence planning. In Scotland, Justice Social Workers complete Level of Service/Case Management Inventory (LS/CMI), SARA v3 and sentence planning. Identification of men can also be done retrospectively.

- Adult (18+) men serving a community sentence or post imprisonment on license for IPV towards a female current or ex-partner
- Drugs or alcohol linked to criminogenic need recorded on OASys (England) or LS/CMI (Scotland)
- Able to provide contact details for (ex)-partner victim of index crime will be invited to participate in the trial
- Able to communicate in and understand English for the purpose of research interviews
- No history of sex offences against children
- Answers 'strongly disagree' to all 8 items on the eHealth Literacy Scale (eHEALS)
- Substance use does not impair ability to take part in the trial using the substance use screen (England) or SARA V3 (Scotland)
- Not suitable for existing probation-based perpetrator interventions
- Not involved with the private family law court

health, social and criminal justice data sets

Figure 3. Study flowchart

Figure 3 illustrates the different phases of the cRCT for male participants.

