3.2.2 EXCLUSION CRITERIA FOR PARTICIPANTS (MEN)

- 1. Suitable for or attending an existing probation-based perpetrator intervention.
- 2. Man involved with the private family law court.
- 3. History of sex offences against children.
- 4. Answers 'strongly disagree' to all 8 items on the eHealth Literacy Scale (eHEALS).
- 5. Substance use impairs ability to take part in the trial (based on practitioner assessment of frequency/amount of substance use, impact of substance use on daily activities/functioning, and health, social, legal or financial problems as a result of substance use) assessed using the substance use screen (England) or SARA V3 (Scotland).

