3.2.4 EXCLUSION CRITERIA FOR CURRENT OR EX-PARTNERS (WOMEN)

- 1. Current order preventing her from contacting current or ex male partner recruited to the trial.
- 2. Other safety concerns that may put the male partner at risk. These will be considered on a case-by-case basis by the research team and the clinical team e.g. where both participants share a mobile phone number, the female participant has a court case pending for IPV or there is a child protection hearing pending.
- 3. Female partner discloses that there is an order preventing her male current or ex-partner from contacting her (i.e. contradicting what he has said in his screening interview). In such cases the man would not be withdrawn, unless the clinical team felt there was an increased risk to either party in his continuing in the study.

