3.4.3 SCREENING & ELIGIBILITY RISK ASSESSMENT FOR MALE PARTICIPANTS

Eligibility screening will be undertaken by PP/ JSW at PDU/ JSWT (Contact 1). During this contact, PP/ JSW will also conduct the risk assessment to determine suitability.

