10.9 POPULATIONS UNDER INVESTIGATION

Men who have been convicted for IPV and received a community sentence.

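### Section 8.2 bars men under no-contact orders and names its own decision-maker, but no eligibility list carries the rule; the Figure 3 checklist also reverses the eHEALS exclusion

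*Protocol*

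**What the plan says.** **Court orders.** Section 8.2, the participant distress protocol, ends with an eligibility rule. It makes ineligible "Participants who have a court order preventing them or someone on their behalf from contacting a current or former partner". This rests on the man's own report in the first instance, confirmed where possible by his partner and the substance use treatment service. The section then adds: "The man's keyworker at the substance use treatment service will make the final decision on whether the man is suitable to take part".

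**Eligibility lists.** Section 3.2.1 has four inclusion criteria for men. Section 3.2.2 has five exclusion criteria, from "Suitable for or attending an existing probation-based perpetrator intervention" through family court involvement, sex offences against children and eHEALS to impairing substance use. The synopsis repeats both lists. None of these items concerns a court order.

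**Who screens.** Section 3.4.3: "Eligibility screening will be undertaken by PP/ JSW at PDU/ JSWT (Contact 1"). Section 3.3 likewise has the probation practitioner or justice social worker screen all men against the criteria.

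**Orders disclosed by the partner.** Section 3.2.4 item 3 excludes the woman if she reports an order against the man that contradicts his screening answer. It continues: "In such cases the man would not be withdrawn, unless the clinical team felt there was an increased risk to either party".

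**eHEALS.** Exclusion criterion 4 in section 3.2.2 reads "Answers 'strongly disagree' to all 8 items on the eHealth Literacy Scale (eHEALS"). Figure 3 prints the same words in its checklist of what makes a man eligible.

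**Population.** Section 10.9 describes "Men who have been convicted for IPV and received a community sentence", whereas 3.2.1 also admits men on licence after prison.

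**The concern.** Eligibility should be readable from one place, and every copy of it should agree. Here a criterion that touches partner safety appears only in a distress protocol, which nobody screening a man has reason to consult for entry rules. Staff working from 3.2, the synopsis or Figure 3 would not apply it; staff who know 8.2 would. Sites could then enrol different kinds of men.

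The decision-maker is also unsettled. Recruitment runs through probation delivery units and justice social work teams. Under section 4.3 substance use treatment is something men may receive; it is not an entry condition. Some men may have no keyworker of the kind 8.2 names, in which case its final decision could not be taken as written.

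The Figure 3 item is a different kind of fault. It sits in a screening checklist, and taken at its word it asks for what the exclusion list forbids.

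**Working it through.** No arithmetic is involved. The check is a comparison of the current text.

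**1. Is the court-order rule in any eligibility list?**

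| Place | Court-order rule for men? | Who decides |
|---|---|---|
| Synopsis | No | Not stated |
| 3.2.1 (4 inclusions) | No | Not stated |
| 3.2.2 (5 exclusions) | No | Practitioner assessment, for the substance use item only |
| Figure 3 (9 items) | No | Probation practitioner or justice social worker |
| 3.3 and 3.4.3 | No | Probation practitioner or justice social worker |
| 8.2 | Yes: ineligible | Keyworker at substance use treatment service |

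The nine Figure 3 items match 3.2.1 and 3.2.2 one for one (4 + 5 = 9), so the checklist has no spare item that could carry the rule.

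**2. How does 3.2.4 item 3 relate to 8.2?** It covers an order that comes to light when the partner contradicts what the man said at screening. Under 3.3 she is approached after his baseline assessment, and under 5.3.2 he counts as enrolled from signing consent. It is therefore a rule for a man already enrolled, while 8.2 is a rule for entry, and the two can stand together. Two things remain unclear. Item 3 presupposes that men are asked about orders at screening, yet no list says so. Section 8.2 relies on the partner's confirmation where possible but gives no consequence if she contradicts him; only 3.2.4 does.

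**3. Is the eHEALS item reversed?** The five exclusions of 3.2.2 as they appear in Figure 3:

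| Exclusion in 3.2.2 | Form in Figure 3 |
|---|---|
| Existing perpetrator intervention | Negated |
| Private family law court | Negated |
| Sex offences against children | Negated |
| Substance use impairs participation | Negated |
| eHEALS, all 8 items 'strongly disagree' | **Not negated** |

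Four of five were turned into conditions to be met. The fifth kept its exclusion wording, so its meaning flips.

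**4. Does 10.9 affect the analysis?** Section 10.9 names only men with a community sentence. Section 10.4.1 defines the primary analysis set as everyone followed up at 4 or 12 months, without reference to sentence type. The description in 10.9 is incomplete, but the analysis set is fixed elsewhere.

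**The case against.** The keyworker wording looks like a remnant of earlier work. The background section says ADVANCE was developed for men in substance misuse treatment, and similar references survive in 3.8.8 (returning tablets) and 8.3 (contacting staff). Section 3.4.3 also has the practitioner carry out a risk assessment of suitability, at which an order might well surface. This explains how the conflict arose but does not remove it: 8.2 is current text, and nothing tells a site to disregard it.

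The eHEALS item is probably an editing slip. The revision history records that version 5 reworded this criterion and moved it from inclusion to exclusion. The synopsis and 3.2.2 both have it as an exclusion, and a practitioner screening for a digital programme would be likely to notice. Only the text of Figure 3 could be read, so its layout is unchecked. That stands, and it is why the claim goes no further than a reversed item needing correction. It does not show that men without digital skills would be selected.

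A reader might also infer that 3.2.4 contradicts 8.2 by keeping a man whom 8.2 bars. The text does not support that, because item 3 deals with an order discovered after he has enrolled.

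**Conclusion.** The point holds on two counts. Section 8.2 sets an entry rule, and a decision-maker, that the operative eligibility sections do not contain; and Figure 3 reverses exclusion criterion 4. Both affect who is enrolled, and the first bears on partner safety. Both are cheap to correct. It should be fixed, but it does not call the design or the analysis into question.

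No numerical size can be attached. The protocol does not give the share of men under no-contact orders or say how many have been screened.

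Two stronger readings are not supported:

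- **That 10.9 removes randomised men on licence from the analysis.** Section 10.4.1 sets the analysis set by follow-up alone, so 10.9 is a wording mismatch.
- **That enrolling men under orders would cost a stated amount of power.** This needs a share of such men and an assumption that they cannot show an effect. The protocol supplies neither. Of the 29 ABI items, 17 are psychological, and nothing in the document shows that an order takes scores to the floor.

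The conclusion assumes that sites screen from section 3.2, the synopsis or Figure 3. Any separate screening form is not in the document and may differ.

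**What to change.** 1. Reconcile 8.2 with 3.2.1, 3.2.2, the synopsis and Figure 3 so that one court-order rule and one named decision-maker appear throughout. No position is taken here on which rule or which decision-maker; that is for the sponsor and the clinical lead.
2. State in 3.2.4 that item 3 governs orders disclosed after the man has enrolled, and cross-refer it to the reconciled rule.
3. In Figure 3, change the eHEALS item to: Does not answer 'strongly disagree' to all 8 eHEALS items.
4. In 10.9, add men on licence after imprisonment, to match 3.2.1. This is a wording alignment only.
5. Check men already screened against the reconciled text, and correct any site screening form that carries the same wording.

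The cost is a protocol text amendment, a re-issued flowchart and a one-off check of screening records. The sample size, randomisation and analysis model are unaffected.
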